5.8. Data management

All data collected during the survey will be held confidentially by UBC. The EDC system used for data collection encrypts all respondent-identifying information, and respondent identifiers are stored separately from the survey responses. No identifiable information will be required from any respondent, but will be collected if they are eligible and wish to receive payment.

The survey is programmed to ensure Internet and telephone respondents cannot skip ahead and will only allow for missing data when caused by skip patterns.

Skip logic as well as the ability to mark only one response or multiple responses are part of the programming for the survey administration and minimize the occurrence of data entry errors. There will be no queries to respondents for this project.

5.9. Data analysis

Data collected from the survey will be reported as descriptive statistics. Frequency distributions with 95% CIs will be calculated for respondent responses to all questions that address the survey objectives. Responses to each question relating to the key safety messages will be categorized as “Correct response” and “Incorrect response”. “I don’t know” is categorized as an incorrect response unless otherwise specified.

In addition to the overall analysis, survey data will be analyzed to determine if there are any differences for HCPs, by medical specialty.

The following will be reported as part of the analysis:

HCPs:

Survey administration

- The number of survey invitations issued by method of distribution and specialty

- The number of survey invitations returned due to incorrect mailing address of HCPs invited to participate in the survey
- The number of HCPs who responded to the invitation to participate in the survey
- The number of HCPs eligible for participation in the survey
- The number of ineligible HCPs along with the reasons for ineligibility
- The number of eligible HCPs who completed the survey

Demographic characteristics of participants

- Distribution of participants by age groups
- Distribution of participants by gender
- Distribution of participants by practice setting
- Distribution of HCP by state
- Distribution of participants by medical specialty
- Distribution of participants by years in medical practice
- Distribution of participants by number of patients treated with Humalog U-200 KwikPen

Responses to questions pertaining to the survey objectives:

- Awareness of the DHPC on the correct use of Humalog U-200 KwikPen
- Understanding of the key safety messages
- Self-reported practices with respect to communication of the key safety messages in clinical practice

Patients:

Survey administration

- The number of invitations distributed
- The number of survey invitations returned due to incorrect mailing address of patients invited to participate in the survey
- The number of patients who responded to the invitation to participate in the survey
- The number of patients eligible for participation in the survey
- The number of ineligible patients along with the reasons for ineligibility
- The number of eligible patients who completed the survey

Demographic characteristics of participants

- Distribution of participants by age groups
- Distribution of participants by gender
- Distribution of patient by state

- Distribution of participants by years with diabetes
- Distribution of participants by length of time treated with any injectable insulin therapy
- Distribution of participants by length of time treated with Humalog U-200 KwikPen
- Distribution of participants by length of time of prior insulin use prior to Humalog U-200 KwikPen

Patient responses to questions pertaining to the survey objectives:

- Awareness of the Important Safety Information for Humalog U-200 KwikPen
- Receipt of or access to Important Safety Information
- Understanding of the key safety messages
- Self-reported practices with respect to the key safety messages

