5.3. Study Endpoints

The additional Risk Minimization Measures will be considered effective if the majority of respondents demonstrate they are aware of the key safety messages communicated.

HCPs:

- Demonstrating that they understand the key safety messages communicated in the DHPC.
- Reporting they discuss the safe use of the product as defined in the product label and DHPC to their patients who are receiving their first prescription of Humalog U-200 KwikPen.

Patients:

- Demonstrating that they understand the key safety messages communicated about Humalog U-200 KwikPen.
- Reporting that they follow the key safety messages during administration of Humalog U-200 KwikPen.

All statistical analyses will be descriptive, i.e., no formal hypothesis will be tested.

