5.4. Setting

The assessment surveys will be executed and the analysis will be completed within 18 months from product launch.

HCPs:

Eligible HCPs will receive an invitation letter ([APPENDIX I.2](#)) via email if an email address is available, or a letter via the United States Postal Service (USPS). The invitation letter will include: an overview of the rationale for the survey, information on how to access the survey online and by telephone, and a unique User Identification to ensure that the invitation is used only once. For telephone interviews, a trained interviewer, working from a computer-assisted telephone interviewing (CATI) script, will read questions or statements to the HCP. The letter will also contain a unique code that the respondent must provide when accessing the survey via the Internet or telephone. For telephone interviews, a trained interviewer, working from a computer-CATI script, will read questions or statements to the HCP. The average survey is expected to take approximately 15 minutes to complete.

A random sample of HCPs will be recruited to participate in the survey based on the list of HCPs to whom Lilly has provided a DHPC letter. The recruitment letter will indicate that participants will be compensated \$100 for their time and effort in completing the survey with the exception of HCPs who are licensed and practice in Minnesota, Vermont, Massachusetts or the District of Columbia in accordance with state laws. HCPs from these states can elect to participate however they will not be paid. Respondent-identifying information will be collected for the purposes of providing payment.

The response rate will be monitored throughout the data collection period. Reminder notices will be sent via email and or via the USPS. Additional recruitment methods may be explored during survey execution if necessary to achieve a total of 280 completed surveys.

Patients:

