5.7. Study size

The target sample sizes for the HCP and patient populations are 280 completed surveys for each population. The size of the sample was determined based on both practical and statistical considerations. There is no target comprehension rate specified *a priori*. A sample of 280 completed surveys for both HCPs and patients will allow estimation of the comprehension rate for each key safety message with a moderately high degree of precision. The table below shows the precision of the estimates for level of understanding using two-sided 95% CIs obtained with the sample size of 280 completed surveys. The noted CIs are used to indicate that for any survey-estimated rate of understanding, the true population rate of understanding is at least as high as the lower limit of the 95% CI and may be as high as the upper limit of the 95% CI.

Equation 1

$$95\%CI = Response\ Rate \pm 1.96 \left\{ \sqrt{\left[\frac{Response\ Rate(1-Response\ Rate)}{Sample\ Size} \right]} \right\}$$

Table 1 Sample size calculations

Sample Size	Observed Response Rate* (e.g. Knowledge)	2-Sided 95% CI		
		Half-width	Lower Limit	Upper Limit
280	50%	5.9%	44.1%	55.9%
	60%	5.7%	54.3%	65.7%
	70%	5.4%	64.6%	75.4%
	80%	4.7%	75.3%	84.7%
	90%	3.5%	86.5%	93.5%

*Percentage of responders who correctly answered a question.

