[DROP DOWN LIST INPUT WITH STATES TABLE, EXCLUDE PREFER NOT TO ANSWER]

[IF RESPONDENT ANSWERS MASSACHUSETTS, MINNESOTA, VERMONT, OR DISTRICT OF COLUMBIA, DISPLAY REMINDER MESSAGE 1 ON SAME PAGE AND GO TO Q4.]

[REMINDER MESSAGE 1]: If you practice and you are licensed in the District of Columbia, Massachusetts, Minnesota, or Vermont just a reminder that we appreciate your participation; however, no compensation for your services will be provided in accordance with local laws.

4. Please choose an option about your participation in this survey.
 - i. ○ I will participate in the survey and provide my contact information.
 - ii. ○ I will participate in the survey but choose not to be paid.

5. Are you involved in the management of patients with diabetes? This includes prescribing medications to treat diabetes or providing education to help manage diabetes.
- Yes
 - No **[GO TO Q7, TERMINATE AFTER Q14]**
6. What is your role in the management of patients with diabetes?
- Physician
 - Nurse Practitioner
 - Physician Assistant
 - Registered Nurse **[GO TO Q8]**
 - Other **[GO TO Q8]**
7. What is your primary medical specialty?
- General Internal Medicine
 - Endocrinology/Diabetology
 - Family Medicine
 - Other
8. How many years have you been in practice as a physician, physician assistant, or nurse since completing your medical/nursing education?
- Less than 5 years
 - 5 – 10 years
 - 11 – 15 years
 - More than 15 years

9. In what type of facility do you work?
- General Practice
 - Hospital
 - Other
10. Are you aware of the insulin product Humalog® U-200 KwikPen®?
- Yes
 - No **[GO TO Q12, TERMINATE AFTER Q14]**
 - I don't know **[GO TO Q12, TERMINATE AFTER Q14]**
11. For how many patients have you prescribed, or managed their treatment with, Humalog® U-200 KwikPen®?
- 0 **[TERMINATE AFTER QUESTION 14 IF 140 OR MORE COMPLETE RESPONDENTS HAVE ANSWERED 0, WHERE 140 IS A CONFIGURABLE NUMBER]**
 - 1 – 5
 - 6 – 10
 - 11 – 20
 - More than 20

12. Have you or any of your immediate family members ever worked for Eli Lilly and Company (Lilly), United BioSource Corporation (UBC), or the Food and Drug Administration (FDA)?

- Yes **[TERMINATE AFTER QUESTION 14]**
- No
- I don't know **[TERMINATE AFTER QUESTION 14]**

13. Which of the following groups best describes your age?

- Less than 30
- 30 – 39
- 40 – 49
- 50 – 59
- 60 – 69
- 70 or older

14. What is your gender?

- Male
- Female

[END SCREENING QUESTIONS]

[BEGIN SURVEY CONTENT]

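### HCPs are to be compared by medical specialty, but the survey never asks registered nurses and 'Other' roles for theirs, so eligible completers drop out of that analysis

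*Protocol*

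**What the plan says.** Section 5.9 adds one breakdown to the overall HCP analysis: "survey data will be analyzed to determine if there are any differences for HCPs, by medical specialty". It also promises the distribution of participants by specialty. Section 5.6 includes medical specialty among the HCP characteristics to be collected and exempts no role.

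In Appendix I.1, Q7 ("What is your primary medical specialty") is the only question that records specialty. Q6, on role, passes physicians, nurse practitioners and physician assistants on to Q7, but sends Registered Nurse and Other to Q8. Neither answer ends the survey. HCPs who answer No at Q5 are routed to Q7 and then terminated after Q14.

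On sampling, section 5.4 says "A random sample of HCPs will be recruited to participate in the survey", drawn from the list of HCPs sent the Direct Healthcare Professional Communication (DHPC). No stratum, quota or minimum by specialty is stated. The only HCP quota is the configurable cap of 140 on respondents with no patients on the product (Q11). Section 5.9 also lists this item for reporting: "The number of survey invitations issued by method of distribution and specialty".

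On size, section 5.7 states: "The target sample sizes for the HCP and patient populations are 280 completed surveys for each population". Table 1 gives precision for the full 280 only.

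**The concern.** The analysis needs a variable that the questionnaire does not collect from two of the five role categories. Those respondents are eligible and count toward the 280, but have no specialty. The routing looks unintended, because HCPs about to be screened out are asked their specialty while some who complete the survey are not.

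More than registered nurses may be affected. Section 3.1 names pharmacists among the DHPC recipients, and Q6 has no pharmacist option, so an eligible pharmacist would have to choose Other and would also skip Q7.

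The gap cannot be closed afterwards from the survey itself. Section 5.8 allows missing data only where skip patterns cause it and rules out queries to respondents. An analysis plan written later cannot recover an answer that was never requested.

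At stake is the completeness and readability of the specialty breakdown. It would describe only part of the HCP sample, and its smallest group may be small enough for a real difference to go unnoticed.

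**Working it through.** **1. The plan's own figure.** Equation 1 in section 5.7 is 1.96·√(p(1−p)/n). With n = 280:
- p = 0.50: 1.96·√(0.25/280) = 5.9 points
- p = 0.80: 1.96·√(0.16/280) = 4.7 points

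Both agree with Table 1, as do its other three rows (5.7, 5.4 and 3.5 points at 60%, 70% and 90%).

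**2. Who has a specialty recorded.** Following the routing in Appendix I.1:

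| Answer | Next question | Stays in the survey? | Specialty recorded? |
|---|---|---|---|
| Q5 No | Q7 | No, terminated after Q14 | Yes |
| Q6 Physician, Nurse Practitioner, Physician Assistant | Q7 | Yes, if otherwise eligible | Yes |
| Q6 Registered Nurse | Q8 | Yes, if otherwise eligible | No |
| Q6 Other | Q8 | Yes, if otherwise eligible | No |

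Sections 5.6 and 5.9 give no exception that would match the last two rows.

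**3. How many could be affected.** The protocol gives no role mix, so the share is an assumption, shown as a range:
- 5%: 0.05 × 280 = 14 without a specialty, 266 with one
- 20%: 0.20 × 280 = 56 without a specialty, 224 with one

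**4. Precision within the smallest specialty.** The specialty mix is not given either. Assume that the smallest specialty is 10% to 20% of 280 respondents and apply Equation 1 to that group:

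| Assumed share | n | Half-width at 50% | Half-width at 80% |
|---|---|---|---|
| 10% | 28 | 1.96·√(0.25/28) = 18.5 | 1.96·√(0.16/28) = 14.8 |
| 20% | 56 | 1.96·√(0.25/56) = 13.1 | 1.96·√(0.16/56) = 10.5 |

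These are about 2.2 to 3.2 times the Table 1 values (13.1/5.9 and 18.5/5.9). If the 10% applied only to 224 classified respondents, the group would be about 22, with half-widths of 20.9 and 16.7 points. Most of the imprecision therefore comes from dividing 280, and the skip adds a little.

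**5. What a proportional draw changes.** If respondents arrived as a simple random sample, the number in a 10% specialty would vary around 28 with a 95% binomial range of 19 to 38; for a 20% specialty, 56 with a range of 43 to 69. Proportional stratification of invitations removes the part of this variation that comes from who is invited. Variation in response and eligibility remains, and the expected count stays at 28 or 56, so the half-widths in step 4 do not improve on average.

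**The case against.** The strongest reply is that this is a descriptive survey ("All statistical analyses will be descriptive, i.e., no formal hypothesis will be tested") whose 280 was chosen for precision in the whole HCP population. No precision is claimed for subgroups, so wide subgroup intervals are to be expected. That stands, and it is why the point is minor.

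The effect of the skip is also unknown and may be small. Section 3.1 does not name registered nurses among the DHPC recipients, so few may be on the list. Pharmacists, if shown Q7 with its present options, would mostly choose Other, which adds little to a comparison of internal medicine, endocrinology and family medicine. Q6 still records role, so the skipped respondents could be shown as a separate category. All of this limits the size of the problem. It does not reconcile the routing with sections 5.6 and 5.9.

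The specialty field that the list appears to hold might be used to fill the gap, but the protocol does not say that it will be linked to responses.

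A reader might infer three stronger points that the document does not support:
- **That the draw is unstratified.** Section 5.4 says only that the sample is random, and reporting invitations by specialty is compatible with drawing by specialty. The accurate statement is that no stratification is stated.
- **That an interval for differences between specialties is missing.** How a descriptive breakdown is contrasted is ordinary analysis-plan content, and that plan is not at hand.
- **That the protocol should allocate equally across specialties.** With assumed list shares of 10%, 40% and 50%, three equal groups give a design effect of (0.10² + 0.40² + 0.50²)/(1/3) = 1.26, which widens the overall half-width at 50% from 5.9 to 5.9·√1.26 = 6.6 points. That trades precision on the main estimates for a secondary breakdown, and its absence is not an error.

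**Conclusion.** The point holds as an inconsistency between the analysis promised in section 5.9, the variable list in section 5.6 and the routing at Q6. Eligible respondents in two role categories will have no specialty and will be absent from the only HCP subgroup analysis named.

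The number affected is 14 to 56 if 5% to 20% of completers are in those roles; both shares are assumptions, and the true figure could lie outside them. Separately, the smallest specialty would have a half-width of about 13.1 to 18.5 points at 50%, or 10.5 to 14.8 at 80%, on the assumption that it makes up 20% to 10% of respondents.

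A reader might conclude that the HCP results as a whole are compromised. They are not: the skipped respondents stay in the overall analysis, and Table 1 is correct for 280. Severity is minor, but the correction has to be made before the survey is launched.

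**What to change.** 1. Remove the skip at Q6 so that every eligible role answers Q7, or replace Q7 with an area-of-practice item whose options fit nurses and pharmacists. Keeping Q7's present options would be simpler, but would gain little for pharmacists. The cost is one extra question for the roles now skipped, plus a small programming change.
2. State in section 5.4 that invitations are drawn proportionally by the specialty field on the list, assuming that the list holds it, as the reporting item in section 5.9 suggests. This needs no more than 280 completed surveys and costs no overall precision. It balances who is invited but does not make a small specialty larger.
3. Add a sentence to section 5.9 or 5.11 saying that precision by specialty is limited at this sample size, and that the absence of a visible difference is not evidence that specialties are alike. This costs nothing.

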5.10. Quality control

Data will be collected using a secure online EDC system that has been developed and fully validated. A rigorous System Development Life Cycle (SDLC) is used for validation that complies with 23 internal IT Standard Operating Procedures (SOPs) of UBC. Unit testing and formal validation occur on all appropriate systems and components during the build stage. The SDLC is fortified with SOPs addressing validation for all clinical and risk minimization-related applications. The Internet-based repository will be used to store survey data and other relevant program information. The system is 21 CFR (Code of Federal Regulations) Part 11 compliant for the entry, storage, manipulation, analysis and transmission of electronic information. This platform ensures compliance with all relevant regulatory guidelines. Respondent-identifying information is stored separately from survey data.

Programming will be reviewed by Quality Control and simulated users [User Acceptance Testing (UAT)] prior to implementation.

At the completion of data collection, data will be extracted from the EDC and mapped to SAS datasets (SAS V9.1.3 or higher) as defined in the application Data Collection Tools (aDCTs). The mapping of raw data will be validated, as will the programming of the analysis datasets created from the raw EDC SAS datasets. The Analysis SAS datasets are used to populate analysis tables that are programmed by using SAS according to the survey analysis plan. The final datasets and table output will be independently validated using SAS, and reviewed by the Quality Assurance Team.

The UBC has an Information Technology Quality Assurance Group that is responsible for managing and overseeing system/application development and validation, as well as related compliance functions.

5.11. Limitations of the research methods

The participants will be self-selected since they will voluntarily respond to the invitation to participate. The survey recruitment strategies will include a random sample of HCPs who received educational outreach, which should be generalizable to the overall HCP population who are educated about the use of Humalog U-200 KwikPen.

Patients will be recruited via the PBM database and will be identified as those patients who have filled/refilled a prescription for Humalog U-200 KwikPen.

Additionally, inherent in survey research is the reliance on the respondent's recall for whether or not the risk minimization communication was received in order to evaluate the scope of risk minimization measures. If the respondent says she/he did not receive the communication, the risk minimization program is evaluated as not optimally disseminating material. It is possible, however, that respondents may simply not recall receiving the tools that were, in fact, received. It is also possible that they have acceptable understanding of the risks and appropriate behaviors despite not receiving or recalling receipt of the risk minimization measure-specific communication. All data from the survey are self-reported and therefore susceptible to possible reporting bias. This is also applicable to the patients' self-reporting of their practice behaviors to minimize the risks. There may be discrepancies between what respondents report about their practices and their actual behaviors.

5.11.1. Controls to minimize bias

A number of controls will be in place to ensure the survey is conducted in a professional manner and to minimize bias, including the following:

- Lists of response options will be randomized to minimize the potential for positional bias.
- The Internet and telephone surveys will be programmed to ensure that questions are asked in the appropriate sequence and all questions will be presented in a standard order to reduce exposure bias. Respondents cannot skip ahead or go back to a question once the question has been answered. All questions presented must be answered in order to complete a survey. Not all questions may be presented due to skip logic within the survey.
- Respondents will be provided with a unique code during the recruitment process and will then be asked to provide the unique code in order to gain access to the Internet-based and telephone administration systems. The code will be inactivated after use to minimize exposure bias and fraud.

6. PROTECTION OF HUMAN SUBJECTS

6.1. Personal Information and Consent

All data collected during the survey will be held confidential by UBC and used only for the purposes stated in the survey instructions. Respondent names and addresses are collected for the purposes of mailing a thank you letter and payment, if applicable, after the survey is completed. The EDC system used for data collection encrypts all identifiable information, and respondent identifiers are stored separately from the survey responses.

By answering the first question of the survey ("*Do you agree to take part in this survey about Humalog® KwikPen®, 200 units/mL (Humalog® U-200 KwikPen®?)*") after reading the introductory message ("Preamble 1"), respondents are acknowledging informed consent for participation in the research study.

If, during survey completion, UBC project personnel are made aware of a safety event, the UBC project personnel will follow the reporting structure described in [Section 7](#). The respondent will

be asked for consent to allow their contact information to be provided to Lilly, so that Lilly may contact them for additional information. If the consent is not granted, UBC personnel will report the Safety Event with the information provided by the respondent.

